## 6. Outcome Measures

- **Primary Outcome:** Proportion of MI oocytes achieving MII maturation within 4 hours.
- **Secondary Outcomes:** Fertilization rates, day 3 embryo quality, day 5 blastocyst quality, implantation rate, and clinical pregnancy rate.

**7. Statistical Considerations** Categorical outcomes will be compared using chi-square or Fisher's exact tests. Logistic regression will adjust for

patient age, AMH, and gonadotropin dose. A p-value  $<0.05$  will be considered statistically significant.

**8. Ethical Considerations** The study will adhere to the Declaration of Helsinki and Good Clinical Practice guidelines. Ethical approval will be obtained prior to enrollment. All participants will provide written informed consent. Confidentiality will be maintained, with data anonymized using unique study codes.

**9. Data Handling and Confidentiality** Data will be stored in secure, password-protected systems. No personally identifiable information will be shared or published.

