## 2. Study Objectives and Endpoints

- **Primary Endpoint:**
  - Proportion of MI oocytes maturing to MII within 4 hours of culture.
- **Secondary Endpoints:**
  - Fertilization rate (percentage of matured MII oocytes achieving normal 2PN post-ICSI)
  - Day 3 and blastocyst embryo quality
  - Implantation rate (number of gestational sacs per embryo transferred)
  - Clinical pregnancy rate (confirmed fetal heartbeat at 8–10 weeks)

**3. Sample Size and Power** A total of 60 patients will be enrolled, based on preliminary estimates indicating that this sample size provides >80% power to detect a 25% difference in maturation rates at a two-sided alpha of 0.05, assuming maturation rates improve from ~40% (control) to ~65% (exosome group).

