## 5. Statistical Methods

- **Primary Analysis:**
  - Compare the proportion of MI oocytes maturing to MII between exosome and standard media using chi-square or Fisher's exact tests.
- **Secondary Analyses:**
  - Compare fertilization rates and embryo quality using similar tests.
  - Implantation and clinical pregnancy rates summarized descriptively and analyzed if numbers permit.
- **Adjustment:** Logistic regression models may adjust for patient age, baseline AMH, and total gonadotropin dose.
- **Significance:** Two-sided tests,  $p<0.05$  considered statistically significant.

**6. Handling of Missing Data** Missing maturation outcomes will be treated conservatively as non-matured. Sensitivity analyses may exclude such oocytes. No imputation planned for secondary reproductive outcomes.

**7. Interim Analyses and Data Monitoring** No formal interim analyses are planned. Data will be reviewed periodically for safety and protocol compliance by the study team.

**8. Reporting Conventions** Descriptive statistics will include means, medians, standard deviations, and ranges. Tables and figures will illustrate maturation rates and embryo development outcomes by intervention.

---

End of Statistical Analysis Plan.

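### The SAP's primary test pools oocytes and ignores patient, leaves chi-square or Fisher open, and makes optional the covariate adjustment that the protocol promises

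*Combined protocol and SAP*

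**What the plan says.** Protocol section 3 (Study Design) allocates each patient's MI oocytes between exosome-enriched and standard media. The SAP's Full Analysis Set (section 4) is made up of oocytes, so the oocyte is the unit of analysis.

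The primary analysis in SAP section 5 (Statistical Methods) is: "Compare the proportion of MI oocytes maturing to MII between exosome and standard media using chi-square or Fisher's exact tests". A separate item in that section reads: "Logistic regression models may adjust for patient age, baseline AMH, and total gonadotropin dose".

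Protocol section 7 (Statistical Considerations) says "Categorical outcomes will be compared using chi-square or Fisher's exact tests", and then "Logistic regression will adjust for" patient age, AMH and gonadotropin dose. It does not say which of these analyses is primary.

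SAP section 3 (Sample Size and Power) states "A total of 60 patients will be enrolled" and that "this sample size provides >80% power to detect a 25% difference in maturation rates" "at a two-sided alpha of 0.05", with rates of about 40% and 65%. Neither document gives the expected number of MI oocytes per patient.

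**The concern.** There are three linked faults.

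- **Patient is ignored.** The two arms share patients, but the primary test treats all oocytes as independent. No analysis in either document has a patient term.
- **The primary test is not fixed.** Two tests are permitted and neither document has a rule for choosing between them. Two statisticians could report different primary p-values from the same data.
- **Adjustment is required in one document and optional in the other.** The protocol commits to it and the SAP permits it. Neither says what follows if adjusted and unadjusted results differ.

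What is at stake is mainly power. One permitted test falls short of the trial's own power claim. Under within-patient allocation, both permitted tests discard information that the design provides.

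**Working it through.** **Inputs.** From SAP section 3: 60 patients, rates 0.40 and 0.65, two-sided alpha 0.05, power >80%. Assumed, because the documents do not say: 1:1 allocation and one MI oocyte per condition per patient, giving 60 per arm.

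**1. Reproducing the stated power.** With a pooled null variance, the mean rate is 0.525 and

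power = Φ{[0.25·√60 − 1.96·√(2·0.525·0.475)] / √(0.40·0.60 + 0.65·0.35)} = Φ{(1.936 − 1.384)/0.684} = Φ(0.808) = 79.0%.

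The size needed for 80% power is (1.384 + 0.8416·0.684)² / 0.25² = 61.4, so 62 per arm. The plan's figure therefore reproduces as 60 per arm with an uncorrected chi-square. With 30 per arm (60 oocytes in all) power is 49.1%, which does not reproduce it.

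**2. The two permitted tests, by exact enumeration at 60 per arm**

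| Test | Power, 40% vs 65% | Type I error at a common 40% |
|---|---|---|
| Pearson chi-square | 80.3% | 5.1% |
| Fisher's exact | 74.7% | 3.2% |

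The gap is 80.3 − 74.7 = 5.6 points, and it puts Fisher below the stated >80%.

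**3. Effect of ignoring patient.** With one oocyte per arm from each of n patients, the variance of the difference in proportions is [p₁(1−p₁) + p₀(1−p₀) − 2·cov]/n, where cov is the within-patient covariance of the two outcomes. The pooled tests omit the −2·cov term. When oocytes from one woman behave alike, cov is positive, the pooled variance is too large and the tests are conservative. At the null with within-patient correlation ρ, the approximate size of chi-square is 2Φ(−1.96/√(1−ρ)), which is below 5% for any ρ > 0.

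**4. Simulation with patient variation.** Settings (all assumptions): 60 women; patient SD 0.8 to 1.3 on the logit scale; covariates explaining 30% to 70% of that variation; two MI oocytes each, or one to four in proportions 30/40/20/10%; marginal rates held at 40% and 65%.

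| Analysis | Power | Null size |
|---|---|---|
| Pooled chi-square | 81% to 84% | about 2.5% to 4.5% |
| Pooled Fisher | 76% to 81% | about 1% to 3% |
| Adjusted logistic, cluster-robust by patient | 82% to 89% | about 4% to 6% |

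The patient-aware model gains roughly 0 to 6 points over chi-square and 4 to 12 over Fisher. Part of this is the type I error rate returning to its nominal level.

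**5. Share due to the covariates.** With cluster-robust errors in both models, adding the three covariates changed power by only about −2 to +1 points, uneven splits included. Accounting for patient supplies most of the gain.

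**6. Does choosing afterwards inflate error?** A second simulation held the conditional odds ratio fixed, with one or two oocytes per condition per patient. It set the log-odds SDs for covariates and for patient at 0, 0.5 or 1 each. Calling the trial positive if any of chi-square, Fisher or ordinary adjusted logistic regression was significant gave a null error of 3.2% to 5.0%. With uneven splits in the settings of step 4, the range was 3.4% to 5.4%, which is within simulation error of 5%. Chi-square and ordinary adjusted logistic regression reached different verdicts in 0% to about 5% of trials.

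**The case against.** The strongest reply is that this is a tidying matter. The SAP clearly labels the unadjusted comparison as primary, and a prespecified unadjusted primary analysis with supporting adjustment is legitimate. The chi-square/Fisher wording is the same in both documents, so on that point they do not conflict. The lowest-powered option, Fisher, makes a positive claim harder to reach. The gain from adjustment depends on patient and covariate variation that the documents do not quantify: with none, chi-square and adjusted logistic regression both had 79.7% simulated power. More oocytes would also remove Fisher's shortfall: at two per condition per patient with no patient variation, its simulated power was 96.2%.

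Much of this stands. A reader might infer three stronger things, and the documents support none of them:

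- **That the documents disagree on which analysis decides the trial.** The protocol never makes regression primary. The conflict is only over whether adjustment is required.
- **That the loose wording allows a false positive by picking the best p-value.** The null error rates in step 6 show no material inflation.
- **That requiring adjustment would by itself recover much power.** Once patient is handled, the covariates add almost nothing.

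What the reply does not answer is that the primary test ignores the within-patient design, remains a choice of two, and under one choice misses the plan's own power figure on the only basis found to reproduce it.

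**Conclusion.** The point holds as a matter of power and consistency, not of error control. The primary analysis does not match the allocation, and the two documents contradict each other on whether adjustment is required.

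The size is modest. Fisher costs 5.6 points of power against chi-square at 60 per arm, and a patient-aware model gains roughly 0 to 6 points over chi-square. The 74.7% rests on 60 independent oocytes per arm. The gains rest on the assumed patient SDs, the assumed oocyte counts and near-even splits within patient. If patients hardly vary, the gain over chi-square is close to nil. The change is still worth making, because it gives one reproducible primary analysis that fits the design, uses covariates the plan already names, and costs only wording.

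**What to change.** 1. In SAP section 5 and protocol section 7, name one primary analysis: logistic regression of MII by 4 hours on medium, age, AMH and total gonadotropin dose, with cluster-robust standard errors by patient. Specify this one method. Do not offer a random-effects model as an alternative, since that would target a different odds ratio and reopen the choice.
2. State the small-sample correction to be used for the robust standard errors, because simulated null size with 60 patients was about 4% to 6%.
3. In the SAP's adjustment item, change *may* to *will*, to agree with the protocol.
4. Remove Fisher's exact test as an option for the primary endpoint in both documents, and keep the unadjusted chi-square as a supportive analysis.

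The cost is a wording change to both documents, made before the data are seen. No new data or patients are needed.

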## 2. Objectives

- **Primary Objective:** To determine if exosome-enriched culture media increases the proportion of MI oocytes maturing to MII within 4 hours compared to standard IVF media.

- **Secondary Objectives:** To assess subsequent fertilization rates, embryo quality, blastocyst development, implantation, and clinical pregnancy rates.

**3. Study Design** A prospective, single-center, randomized controlled trial. Patients will undergo standard ovarian stimulation protocols. Retrieved MI oocytes will be allocated within each patient to two different culture conditions: exosome-enriched media vs. standard media.

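### The trial is sized on a 25-point difference in maturation, but the plan names no effect measure and no confidence interval that allows for oocytes split within each woman

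*Combined protocol and SAP*

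**What the plan says.** - **Sizing (SAP 3).** "A total of 60 patients will be enrolled", said to give ">80% power to detect a 25% difference in maturation rates" at a "two-sided alpha of 0.05". The assumed rates are about 40% on standard medium and about 65% with exosomes, so the 25% is a difference in percentage points. No number of MI oocytes is given.
- **Allocation (Protocol 3).** "Retrieved MI oocytes will be allocated within each patient to two different culture conditions". The split ratio is not stated.
- **Unit of analysis (SAP 4).** The full analysis set consists of oocytes, not women.
- **Primary analysis (SAP 5).** "Compare the proportion of MI oocytes maturing to MII between exosome and standard media using" a chi-square or Fisher's exact test, judged two-sided at 0.05. Protocol 7 names the same tests and threshold.
- **Regression.** Logistic regression for age, AMH and gonadotropin dose is optional in SAP 5 and planned in Protocol 7. Neither says what the model will report.
- **Reporting (SAP 8).** "Descriptive statistics will include means, medians, standard deviations, and ranges". The next sentence commits to tables and figures of maturation rates and embryo outcomes by intervention.

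Neither document mentions a confidence interval, risk difference, risk ratio or odds ratio for any endpoint.

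**The concern.** The quantity that justified the sample size is a difference in percentage points, yet the plan commits only to a test and to two displayed rates. A p-value below 0.05 does not say whether the data fit an effect near the planned 25 points or one close to zero. A p-value above 0.05 does not say whether 25 points has been ruled out. Both questions need an interval.

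The gap would matter less if a reader could fill it from the published totals. Here that fails. Each woman's oocytes are divided between the two media, so the two proportions share women and are not independent. An interval that respects this needs the woman-level data, which only the investigators will have. They must plan it in advance.

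**Working it through.** **Inputs.** From SAP 3: rates 0.40 and 0.65, 60 patients, two-sided 0.05. Assumed, because the documents do not say: the number of oocytes per medium (30, 60 or 120) and a 1:1 split.

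**1. The plan's own power figure.** Take one independent oocyte per medium per woman, so n = 60 per medium.
- Standard error under the null, with pooled rate 0.525: √(2 × 0.525 × 0.475 / 60) = 0.0912.
- Standard error under the alternative: √((0.40 × 0.60 + 0.65 × 0.35) / 60) = √(0.4675 / 60) = 0.0883.
- Power = Φ((0.25 − 1.96 × 0.0912) / 0.0883) = Φ(0.81) = 79%.
- The unpooled version gives 80.9%, exact chi-square 80.3% and Fisher's exact test 74.7%.

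The stated figure is thus roughly reproduced by chi-square at 60 oocytes per medium, which makes 60 a reasonable central case.

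**2. Precision of an observed 25 points.** Half-width = 1.96 × √(0.4675 / n), oocytes treated as independent.

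| Oocytes per medium | Half-width (points) | 95% CI (points) |
|---|---|---|
| 30 | 24.5 | 0.5 to 49.5 |
| 60 | 17.3 | 7.7 to 42.3 |
| 120 | 12.2 | 12.8 to 37.2 |

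**3. What a bare p-value would hide, at 60 per medium with 24/60 on standard medium.**
- *Non-significant.* 33/60 gives +15 points and chi-square p = 0.10. The standard error is √((0.55 × 0.45 + 0.40 × 0.60) / 60) = 0.0901, so the interval is 15 ± 17.7, or -2.7 to +32.7. It contains both 0 and 25.
- *Borderline.* 35/60 gives +18.3 points with interval +0.7 to +35.9. Uncorrected chi-square gives p = 0.045 and Fisher p = 0.067. SAP 5 allows either test, so the same data could be called significant or not. Under Fisher the first significant count is 36/60 (p = 0.044; interval +2.5 to +37.5).

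**4. Why the totals are not enough.** Suppose 60 women each give one oocyte to each medium, with within-woman correlation ρ. The share of women in whom both oocytes mature is p11 = 0.26 + ρ√(0.24 × 0.2275), the share discordant is ψ = 1.05 − 2p11, and the half-width is 1.96 × √((ψ − 0.25²) / 60).

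| ρ (assumed) | Half-width (points) |
|---|---|
| 0 | 17.3 |
| 0.1 | 16.4 |
| 0.3 | 14.5 |
| 0.5 | 12.2 |

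The totals are the same in every row, yet the valid half-width runs from 17.3 to 12.2 points. A simulation with a 1:1 split, no true effect and an assumed woman-level SD of 1 to 2 logits agrees: the independent-oocyte standard error was roughly 10% to 26% too large, and the type I error of the oocyte-level chi-square fell from 5% to about 3% and 1.4%. In these settings the naive interval is too wide. Uneven splits, or an effect that differs between women, could change the size or direction of the error; that was not quantified.

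**The case against.** SAP 8 does promise rates by intervention, so the size of the effect can be found by subtraction. A reader might infer that results cannot be sized at all, or that p-values are the only planned output. The documents do not support either reading: what is missing is the named measure and its precision.

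A reader might also infer that the only estimate will be an optional odds ratio. No document names an odds ratio, and the regression that is optional in SAP 5 is planned in Protocol 7.

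The quoted SAP 8 sentence is not itself an error. Its wording is not exhaustive, and it suits age, AMH and dose. A plain interval could also be added at reporting without new data. These points stand, and they limit the criticism.

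The widths rest on assumed oocyte counts, and those in steps 2 and 3 also on independence. That is fair, and they are offered as a range, not a forecast. It may also be tempting to extend the point to low power for fertilization. That would need fertilization rates that the documents do not give, and it concerns power rather than reporting.

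What the objection does not answer is that a valid interval depends on woman-level data and on a method chosen beforehand. A plain interval added later from the totals would not meet that need.

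**Conclusion.** The point holds in this form. The trial is sized on an absolute 25-point difference, the primary conclusion is drawn from an oocyte-level p-value, and no effect measure or interval is planned. Rates by medium will be shown, but an interval built from them would ignore the allocation within women.

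At the central assumption of 60 oocytes per medium, the unplanned uncertainty is about ±17 points around an observed 25, and about ±12 to ±24.5 over 120 down to 30 oocytes per medium. Allowing for the woman could narrow it materially under a 1:1 split. The test can still be run as written, so this is a change that should be made, not one on which the trial's validity turns.

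**What to change.** In SAP 5 and SAP 8, for maturation and every other endpoint compared between media:

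- Report n/N per medium and the exosome-minus-standard difference in percentage points, with a two-sided 95% confidence interval that allows for oocytes from the same woman. One suitable method is the marginal difference from a regression model with variance clustered on the woman.
- State the primary conclusion from that interval, in relation to 0 and to the planned 25 points.
- Keep means, medians, SDs and ranges for continuous variables such as age, AMH and dose.

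The cost is SAP wording and one extra output per endpoint. No further patients or outcome data are needed, provided each oocyte record carries the woman's study code. The downside is that the result may look less certain than a bare p-value.
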